### 5.4 Statistical models

#### 5.4.1 Primary analysis

Not applicable.

#### 5.4.2 Key secondary analysis

### 5.5 Not applicable. Rule of exclusion criteria of analysis sets

**Table 5-2 Criteria for exclusion from analysis sets**

Deviation ID	Description of Deviation	Exclusion from
OTH10	Patient was rescreened but did not sign a new ICF	All analysis sets
TRT05	No drug taken after randomization	SAF
INCL01	ICF not signed	All analysis sets

## 5.6 Other statistical aspects

### Secondary efficacy endpoints

Multiple imputation is adopted to impute missing Week 48 biopsy results for eligible patients. See Section 5.1.4 for more details.

CMH test is adopted for inference controlled for the baseline fibrosis stage (F2/F3). In order to pool results from multiple imputation, test statistic of CMH test is transformed using Wilson-Hilferty transformation

$$ST_{WH\_CMH^{(m)}} = \frac{\sqrt[3]{CMH^{(m)}/df} - (1 - \frac{2}{9 * df})}{\sqrt[2]{2/(9 * df)}}$$

Where  $CMH^{(m)}$  is the CMH test statistic computed from the  $m$ -th imputed dataset,  $df$  is the degrees of freedom associated with the test statistic, and  $ST_{WH\_CMH^{(m)}}$  follows approximately standard normal distribution. Consequently, the test results obtained from multiple imputation datasets can be combined by specifying the model effects and standard error in PROC MIANALYZE in SAS and the final one-side  $p$ -value for CMH test can be obtained.

Odds ratio and relative risk obtained from PROC FREQ also need to be transformed to normal distribution before pooling. Both statistics are log-normally distributed and hence a simple log transformation would transform them to normal and similar procedure to the above can be followed to obtain the pooled results. Finally, exponential transformation is implemented to transform the statistics and their CI back to the original scale.

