9.5 Analysis of secondary variables

9.5.1 Efficacy variables

An overview of the secondary efficacy variables and planned analysis is given in [Table 9-2](#).

Table 9-2 Secondary efficacy variables and analyses

Variable	Analysis
At least a one point improvement of fibrosis	Cochran-Mantel-Haenszel test controlling for baseline fibrosis stage for each tropifexor + CVC combination vs. each monotherapy treatment, with supporting information from risk differences, odds ratios with 95% confidence intervals
Resolution of steatohepatitis (as determined by central pathologist)	Cochran-Mantel-Haenszel controlling for baseline fibrosis stage for each tropifexor + CVC combination vs. each monotherapy treatment, with supporting information from risk differences, odds ratios with 95% confidence intervals

There is a single secondary objective in this study which is to characterize the efficacy of tropifexor + CVC in patients with NASH with fibrosis stage F2/F3 as assessed by histological improvement after 48 weeks of treatment compared to monotherapies (tropifexor and CVC) relative to baseline biopsy. There are two estimands that will be used to evaluate this objective.

The first estimand is the difference on the proportion of patients on the different tropifexor + CVC regimens who achieve at least a one point improvement in fibrosis at Week 48 compared to tropifexor and CVC monotherapy patients. It is assumed that anyone who does not have a Week 48 liver biopsy or does not remain on their randomized study treatment for at least 24 weeks (even if a Week 48 biopsy was obtained) will have their outcome imputed by multiple imputation (MI). For subjects who remain on their randomized study treatment for at least 24 weeks, but discontinue study treatment prior to Week 48, available Week 48 biopsy results will be used as observed. This is a hypothetical strategy addressing the question “what would be the outcome if subjects had stayed at least 24 weeks on treatment and a Week 48 biopsy had been obtained”. Treatment differences between tropifexor + CVC combination therapy and monotherapy with tropifexor or CVC will be evaluated using a Cochran-Mantel-Haenszel test controlling for baseline fibrosis stage (F2/F3). The estimand will be evaluated in the FAS population.

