### 2.7.2 Statistical hypothesis, model, and method of analysis

The two secondary endpoints are incorporated in two estimands.

The first estimand is defined as below:

- Treatment: The randomized treatment (tropifexor 140 µg once-daily, CVC 150 mg once-daily, tropifexor 140 µg + CVC 150 mg once-daily, and tropifexor 90 µg + CVC 150 mg once-daily) taken for 48 weeks, further defined in Section 5.2 in the protocol.
- Population: Full analysis set.
- Endpoint: Proportion of patients who have at least a one-point improvement in fibrosis.
- Summary measure: Difference in the proportion of patients on the different tropifexor + CVC regimens who achieve at least a one-point improvement in fibrosis at Week 48 biopsy compared to tropifexor and CVC monotherapy patients.

The second estimand is the same as the first one except

- Endpoint: Proportion of patients with resolution of steatohepatitis

- Summary measure: Difference in the proportion of patients on the different tropifexor + CVC regimens who achieve resolution of steatohepatitis at Week 48 relative to baseline compared to tropifexor and CVC monotherapy patients.

Both estimands will be evaluated using a Cochran-Mantel-Haenszel test controlling for baseline fibrosis stage (F2/F3). Risk differences and odds ratios with 95% confidence intervals will provide supporting information for both estimands.

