### **Risk difference and $100(1 - \alpha)\%$ confidence interval**

For an investigational drug group with  $n_1$  patients at risk, independent from placebo with  $n_0$  patients at risk, of whom  $x_1$  and  $x_0$  experience a certain event, the risk difference is estimated as  $p_1 - p_0$  with  $p_1 = x_1/n_1$  and  $p_0 = x_0/n_0$ . Exact unconditional confidence limits for the risk difference will be obtained with SAS procedure PROC FREQ and option RISKDIFF in the TABLES statement, specifying the RISKDIFF option also in the EXACT statement. In case that exact method fails to produce valid results, asymptotic approach should be adopted. EXACT statement is not to be used in combination with multiple imputation, in which case asymptotic approach is adopted.

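### The test of the biopsy endpoints is stratified by fibrosis stage, but the only risk-difference estimator in the SAP is crude, and the pooling text names relative risk instead of the risk difference

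*SAP*

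**What the plan says.** SAP 2.7.2 gives the summary measure of the first estimand as "Difference in the proportion of patients on the different tropifexor + CVC regimens who achieve at least a one-point improvement in fibrosis", each combination against each monotherapy. The second estimand does the same for resolution of steatohepatitis. Both are tested by CMH, controlling for baseline stage F2 or F3. The same section adds: "Risk differences and odds ratios with 95% confidence intervals will provide supporting information for both estimands". Protocol Table 9-2 lists the same two measures: "with supporting information from risk differences, odds ratios with 95% confidence intervals". Neither place lists relative risk.

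The estimators are in SAP 5.6. The risk difference is p1 - p0 with p1 = x1/n1 and p0 = x0/n0, and "Exact unconditional confidence limits for the risk difference will be obtained with SAS procedure PROC FREQ and option RISKDIFF in the TABLES statement". No strata, weights or common risk difference are mentioned. The paragraph ends: "EXACT statement is not to be used in combination with multiple imputation, in which case asymptotic approach is adopted". The visible text plans multiple imputation only for biopsy outcomes, so this sentence ties the paragraph to the secondary endpoints. The odds-ratio paragraph also starts from a crude formula but allows EXACT COMOR, a common odds ratio across strata. Both paragraphs describe the comparator as placebo, and the trial has no placebo arm.

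For pooling over imputations, SAP 5.6 covers the CMH statistic and then says: "Odds ratio and relative risk obtained from PROC FREQ also need to be transformed to normal distribution before pooling".

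**The concern.** The plan treats fibrosis stage as important enough to stratify the test, but leaves it out of the estimate that the estimand defines. If stage predicts response and the arms differ by chance in their share of F3 patients, that imbalance stays in the crude difference and is removed from the test. The reported interval and p-value can then lead to different conclusions about the same comparison.

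Nothing visible shows that randomization balances stage. The stratification factor is redacted, and SAP 2.1 describes it as an optional assessment that is not a baseline characteristic. The study has no pre-specified hypotheses, so readers will rely largely on the estimates and their intervals. The text also leaves open which risk difference is meant and how it is pooled, so two programmers could follow it and report different numbers.

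**Working it through.** **Inputs from the documents.** Response rates are 69% for the combination, 42% for tropifexor and 35% for CVC (SAP 3.2), so the planned differences are 69 - 42 = 27 and 69 - 35 = 34 points. The plan has 50 per arm. Protocol Amendment 3 reports 193 randomized, and 193/4 = 48.25, so 48 per arm is used below where stated.

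**Assumptions not in the documents.** Half the patients are F3, stage is not balanced by randomization, the F3-F2 response gap is 0 to 30 points, the treatment effect is the same in both stages, and data are complete.

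**The plan's own figures.** Continuity-corrected power at 50 per arm and two-sided 0.10 recomputes as 95.1% for 69% vs 35% (stated 95%) and 81.7% for 69% vs 42% (stated 81%). The inputs are therefore read correctly. The point itself does not rest on these figures.

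**Formulas.** The crude difference is x1/n1 - x0/n0 over both stages. The Mantel-Haenszel difference is the sum of w·d over the sum of w, where d is the difference within a stage and w = n1·n0/(n1 + n0) for that stage.

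**Worked example.** Take 50 per arm, 69% vs 42%, a 20-point stage gap, and F3 in 20 of 50 combination and 30 of 50 tropifexor patients.
- Rates by stage (F2, F3): combination 59% and 79%; tropifexor 32% and 52%.
- Combination: 30 × 0.59 + 20 × 0.79 = 33.5 responders, 67.0%.
- Tropifexor: 20 × 0.32 + 30 × 0.52 = 22.0 responders, 44.0%.
- Crude difference: 67.0 - 44.0 = 23.0 points (95% CI 4.0 to 42.0).
- Stratified: w = 30 × 20/50 = 12 in each stage and d = 27 points in each, so 27.0 points (8.5 to 45.5). CMH p = 0.0077.

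The crude figure is 4 points below the true 27; the stratified figure recovers it.

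**How often imbalance arises.** With 48 per arm the standard deviation of the difference in F3 share is √(2 × 0.25/48) = 0.102. A gap of 15 points is 0.15/0.102 = 1.47 standard deviations. By simulation, 15 points or more occurs in about 13% of comparisons.

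**Effect of the stage gap** (200,000 simulated trials per row, 50 per arm, 27-point difference, 95% intervals against CMH at 0.05, Greenland-Robins variance for the stratified difference):

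| F3-F2 gap (points) | 95th percentile of absolute crude minus stratified (points) | Crude disagrees with CMH | Stratified disagrees with CMH |
|---|---|---|---|
| 0 | 2.1 | 2.0% | 1.4% |
| 10 | 3.0 | 2.7% | 1.5% |
| 20 | 4.6 | 4.5% | 1.8% |
| 30 | 6.3 | 7.0% | 1.7% |

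**Effect of the true difference** (48 per arm, gap 20 to 30 points, 90% and 95% levels matched to the test, Sato variance):

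| True difference (points) | Crude disagrees with CMH |
|---|---|
| 20 | about 6-10% |
| 27 (planned, vs tropifexor) | about 4-8% |
| 34 (planned, vs CVC) | about 1-4% |

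Over these rows the stratified difference disagrees in about 0.2-2%, and crude and stratified differences are more than about 5 to 7 points apart in 5% of comparisons. The standard error is about 1.5-4.5% smaller with stratification. If stage is not prognostic it is about 0.5% larger.

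Levels are matched on purpose. The SAP's 95% intervals and the 0.10 level in its power section differ, and that would add disagreement of its own.

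**The case against.** A reader might infer that the crude difference is biased or is the wrong estimator for this estimand. The documents do not support that. SAP 2.7.2 defines a difference in proportions in the full analysis set without conditioning on stage, and p1 - p0 is unbiased for it under randomization. In the simulations the crude and stratified means agree.

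A reader might also infer that estimate and test will often point in opposite directions. They will not. The disagreement is about significance near the boundary. The two differences have opposite signs in under 1% of trials at true differences of 20 to 34 points (1.2% at most, at 18 points with a 30-point gap). Some disagreement would remain without any stage effect: at 48 per arm and 27 points it is 1.7-3.2% with no gap. The stage gap drives the rest, and its size is assumed.

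The pooling omission is small. The sentence concerns statistics that need a transformation. A risk difference needs none, PROC MIANALYZE is already named, and asymptotic limits are already specified under imputation. The odds-ratio text already allows a common odds ratio. The placebo wording looks like generic text, because SAP 2.7.2 names the comparators. The endpoints are secondary, and both documents call the risk differences supporting information.

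All of this stands as a limit on size. It does not settle which risk difference will be reported, or why an unplanned measure has a pooling rule when the estimand's own measure is not mentioned.

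**Conclusion.** The point holds as one of precision, coherence and complete specification, not of bias. The text is clear: stratified test, crude estimator, and pooling wording that does not match the planned measures. The size depends on an assumed 20 to 30 point stage gap and a half-and-half F2/F3 split. Under those, disagreement on significance is moderate at a 20-point effect and falls as the effect grows to the planned 27 and 34 points. At a 10-point gap and a 27-point effect it is only 2.6-3.2%, and stratification gains no precision. The change is worth making because stage is already collected and already used in the test.

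**What to change.** In SAP 2.7.2 and 5.6:
- Report the Mantel-Haenszel risk difference stratified by baseline F2/F3, with Sato variance, and pool it untransformed by Rubin's rules.
- Confirm that the odds ratio is the stage-stratified common odds ratio that SAP 5.6 already allows, pooled on the log scale.
- Delete relative risk, or list it as a measure in 2.7.2.
- Replace placebo by the monotherapy comparator in the risk-difference and odds-ratio paragraphs.

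The cost is a few lines of text and code, with no new data. There are two small downsides. If stage is not prognostic, the standard error rises by about 0.5%. If the effect differs by stage, the Mantel-Haenszel difference is a weighted average that need not equal the overall difference in proportions. Protocol 1.1 reports greater CVC benefit at higher baseline fibrosis stage, so the SAP should state that interpretation.

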### Repeated measurements

For inference of repeated measurements, PROC MIXED with REML option is employed for MMRM model. The model will include treatment group, visit, interaction between treatment group and visit, and baseline value of the variable of interest and its interaction with visit. The model will adopt unstructured covariance matrix and the degrees-of-freedom method of Kenward and Roger. The difference in the variable of interest between treatment groups and its CI will be calculated using LSMEANS statement.

### Crude incidence and related risk estimates

For  $n$  patients each at risk to experience a certain event with probability  $\pi$ , the crude incidence is estimated as  $p=x/n$ , where  $x$  is the number of patients with the event.

### Odds ratio and $100(1 - \alpha)\%$ confidence interval

For an investigational drug group with  $n_1$  patients at risk, independent from placebo with  $n_0$  patients at risk, of whom  $x_1$  and  $x_0$  experience a certain event with probability  $\pi_1$  and  $\pi_0$  respectively, the odds ratio is estimated as  $\frac{p_1/(1-p_1)}{p_0/(1-p_0)}$  with  $p_1 = x_1/n_1$  and  $p_0 = x_0/n_0$ . A conditional exact  $100(1 - \alpha)\%$  confidence interval will be obtained by using the SAS procedure PROC FREQ with statement EXACT OR or EXACT COMOR. In case that exact method fails to produce valid results, asymptotic approach should be adopted. EXACT

statement is not to be used in combination with multiple imputation, in which case asymptotic approach is adopted.

### **Risk difference and $100(1 - \alpha)\%$ confidence interval**

For an investigational drug group with  $n_1$  patients at risk, independent from placebo with  $n_0$  patients at risk, of whom  $x_1$  and  $x_0$  experience a certain event, the risk difference is estimated as  $p_1 - p_0$  with  $p_1 = x_1/n_1$  and  $p_0 = x_0/n_0$ . Exact unconditional confidence limits for the risk difference will be obtained with SAS procedure PROC FREQ and option RISKDIFF in the TABLES statement, specifying the RISKDIFF option also in the EXACT statement. In case that exact method fails to produce valid results, asymptotic approach should be adopted. EXACT statement is not to be used in combination with multiple imputation, in which case asymptotic approach is adopted.

### **Geometric mean and coefficient of variation**

The geometric mean (where applicable) will be presented for the baseline values, absolute post-dose values and for the ratio to baseline (or pre-dose, respectively) values. The geometric mean of the ratio to baseline will be presented in terms of % change from baseline and will be calculated as follows:  $(\exp(\text{mean of the log-transformed ratio to baseline values}) - 1) * 100$ .

The Coefficient of Variation (CV) will be calculated for the baseline values, the absolute post-dose values and the ratio to baseline (or pre-dose, respectively) values.

